11. ECONOMIC EVALUATION

A formal economic evaluation will be undertaken to assess the relative cost-effectiveness of the PFMT + pessary compared to PFMT only.

11.1 Collection of resources use and data

Resource use data collected will include both primary and secondary care NHS services used by participants. A resource use questionnaire will be designed for self-completion by participants at baseline, 6 and 12 months to record resource use over the trial period.

Healthcare resources required for the delivery of the PFMT and pessary care will be recorded at each centre. Details of the PFMT and pessary care delivered for each participant will be recorded by centre staff.

11.2 Participant level costs

The Participant Resource Use Questionnaire will be used to collect data on use of primary and secondary care services this will include; GP, Nurse, Physiotherapy, Outpatient, Inpatient Stay, Emergency or Unplanned service use (A&E, NHS 24/111)) and medication related to prolapse

IRAS ID: 338183 PEPPY protocol version 3.0 26/02/2025 ISRCTN: xxxxxx Page 29 of 51

symptoms. Data will be self-report with participants asked to state if they have used the service in the time since the proceeding questionnaire (1 month pre baseline questionnaire) and if yes how many times.

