- Vaginal irritation/discomfort
- Granulation of vaginal tissue
- Involuntary expulsion of pessary
- Vaginal smell
- Vaginal discharge
- Vaginal infection
- Vaginal bleeding
- Psychological distress due to vaginal assessment (e.g. as a result of previous abuse or distressing labour)
- Pessary entrapment in the vagina requiring removal in theatre
- Urinary retention requiring catheterisation
- Faecal impaction requiring hospital intervention
- Fistula: recto-vaginal or vesico-vaginal
- Vaginal cancer
- Ureteric obstruction

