8.3.3 Recording AEs and SAEs

Adverse events will be recorded in the case report forms (CRFs) or questionnaires. The local Investigator (or delegate) should then record all relevant SAEs on the SAE form.

In addition, death for any cause (related or otherwise) is recorded on the SAE form.

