11.4 Cost effectiveness

The economic evaluation will be conducted from an NHS perspective. All resource use will be valued in monetary terms using appropriate unit costs. Unit costs for primary and secondary care resources will be taken from the PSSRU Unit Costs of Health and Social Care publication [39]. Any medications used by participants will be valued using the British National Formulary [40]. Total and mean cost per participant will be calculated for each group using methods to account for uncertainty around the mean estimates of costs [41].

Quality Adjusted Life Years (QALYs) will be calculated from EQ-5D-5L data using the recommended tariff values [28].

The primary economic evaluation will be a within trial cost utility analysis. Analysis will be completed as intention to treat, based on randomised group. Costs and QALYs will be combined to calculate the incremental cost per QALY gained along with the incremental net benefit [42].

In addition, a Markov decision model with a monthly cycle will be employed to evaluate effects of the intervention on costs, QALYs and cost-effectiveness over a 5-year horizon. Trial data will be supplemented with data from our existing studies of PFMT and pessary for prolapse [5,6,21] to develop the health states and identify suitable transition probabilities. All costs and outcomes beyond 1 year will be discounted at 3.5% [43].

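### Section 11.2 collects only medication for prolapse symptoms while Section 11.4 values any medication used, so drugs for treatment side effects may go uncosted

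*Protocol*

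**What the plan says.** Section 11.1 describes two sources of resource-use data. The first is self-report: "A resource use questionnaire will be designed for self-completion by participants at baseline, 6 and 12 months". The second is the centre: "Details of the PFMT and pessary care delivered for each participant will be recorded by centre staff".

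Section 11.2 gives the content of the self-report form. It covers "use of primary and secondary care services this will include; GP, Nurse, Physiotherapy, Outpatient, Inpatient Stay", then "Emergency or Unplanned service use (A&E, NHS 24/111)) and medication related to prolapse". The sentence runs over a page break and its last word is symptoms, so the medication item as described covers drugs for prolapse symptoms.

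Section 11.4 adopts an NHS perspective and states "All resource use will be valued in monetary terms using appropriate unit costs". After naming the price source for services it adds "Any medications used by participants will be valued using the British National Formulary".

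Section 8.2 gives the expected adverse events of PFMT and pessary use. "Vaginal infection" is on the list, as are vaginal discharge, bleeding, irritation or discomfort, and granulation. The protocol describes these events as unlikely. On where they are captured, Section 8.3.3 says "Adverse events will be recorded in the case report forms (CRFs) or questionnaires".

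**The concern.** A drug that is never asked about cannot be valued, whatever Section 11.4 says. If the form follows Section 11.2 literally, a woman who took medication for a vaginal infection while wearing a pessary would have no reason to report it, because the infection is not a prolapse symptom.

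Only the intervention arm is allocated a pessary (Section 5.2), and women are asked to use it for at least 16 weeks and may continue (Section 5.1). Side effects of wearing a pessary should therefore be more common in that arm, and so should any missed drug cost. The incremental cost would be too low, the cost per QALY and the incremental net benefit would lean towards PFMT plus pessary, and the same trial costs could carry into the 5-year model. Drugs not recorded at 6 and 12 months are hard to recover later, and no analysis plan can value data that were not collected.

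**Working it through.** The plan states no figure on this point, so there is none to reproduce. The check is a comparison of the sections, followed by an illustration of size.

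**1. Are treatment side effects prolapse symptoms in this protocol's terms?** No. Section 8.1 says that signs or symptoms of the disease under study are not adverse events. Section 8.2 exempts pelvic floor symptoms from adverse event reporting because they are already outcomes, and it lists vaginal infection, discharge, bleeding and irritation as expected adverse events. On these definitions, a drug for one of those events falls outside the Section 11.2 item.

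**2. Does another stated route collect those drugs for costing?**
- Centre records (Section 11.1) cover the PFMT and pessary care delivered. Drugs are not mentioned, and a GP prescription would not obviously appear there.
- Adverse event records (Section 8.3.3) hold events. No link to drugs or to costing is stated.
- The participant diary (Section 5.1) records pessary complications. Section 11 does not name it as a costing source.

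Section 11.2 is the only place where the protocol says medication is collected.

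**3. Direction.** Let d be the drug cost missed per woman in the pessary arm minus that missed per woman in the control arm. Incremental net benefit is (threshold × incremental QALYs) − incremental cost. If incremental cost is too low by d, net benefit is too high by d, pound for pound. Omissions that occur equally in both arms, for example drugs for muscle soreness or low back pain from PFMT, cancel.

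**4. Size, on assumed inputs.** The protocol gives neither rates of drug-treated side effects nor prices.

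d = excess share of women treated × courses per woman × cost per course

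- Lowest: 0.05 × 1 × £5 = £0.25
- A lower-middle case: 0.15 × 1 × £15 = £2.25
- An upper-middle case: 0.30 × 2 × £15 = £9.00
- Highest: 0.50 × 2 × £30 = £30.00

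The upper end is generous. Section 9.1 allows for 40% of pessary fittings not succeeding. If only successfully fitted women had drug-treated side effects, an excess of 50% among all women allocated a pessary would need 0.50 / 0.60 = 83% of the fitted women to be treated, for events the protocol calls unlikely.

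The protocol gives no unit costs for the pessary or for its fitting, review and removal appointments, so d cannot be expressed as a share of the incremental cost.

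**The case against.** The strongest reply is that this is loose drafting with little consequence. Its parts have different weight.

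- **No questionnaire item exists yet.** Section 11.1 says the form will be designed, and Section 11.2 is a short summary introduced as an inclusive list. This stands. It also means the wording can still be settled at almost no cost.
- **Section 11.4 may only name the price source.** The sentence follows the one naming the source of service unit costs, so it can be read as pricing whatever medication is recorded. This is a fair reading, and for that reason the point is an unreconciled scope and not a flat contradiction. It does not remove the gap, because an NHS-perspective costing of these treatments still needs the drugs used for their side effects.
- **Other records may catch some drugs.** Centre staff may note them, adverse events are asked about at every appointment and in follow-up questionnaires (Section 8.3.1), and some women will report them anyway. A reader might infer that these drugs will certainly go uncosted. The documents support only that they may, since no section excludes the other routes or assigns them the task.
- **The arm contrast is diluted.** Some fittings will fail, control women may take up other prolapse treatment (Section 6.2), and women who receive the other arm's treatment stay in follow-up (Section 7.5). A reader might infer a fixed direction of bias. Only a tendency can be claimed.
- **Service contacts.** A reader might take the restriction to prolapse symptoms as applying to GP, nurse, outpatient, inpatient and emergency use as well. That reading is strained: the phrase attaches to medication, and Section 11.1 describes NHS services used by participants without restriction. No missed service cost is counted here.

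**Conclusion.** The mismatch between Sections 11.2 and 11.4 is real. As written, the plan need not collect medication for treatment side effects, and any omission would tend to understate the cost of PFMT plus pessary. The tendency rests on side effects being more frequent in the arm allocated a pessary, and on centre, adverse event and diary records not filling the gap.

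The documents do not give the size. The assumed range is about £0.25 to £30 per woman in the pessary arm, probably towards the lower part. A reader might go further and conclude that the pessary arm will wrongly appear cheaper or cost-effective. The documents do not support this: they contain no rates, drug prices or pessary costs from which a changed conclusion could be shown. This is a minor point, worth correcting because the correction is nearly free and removes a bias that leans one way.

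**What to change.** In Section 11.2 and on the form, change only the medication phrase, to *medication related to prolapse or its treatment, including side effects*, and ask it identically in both arms. Leave the service items (GP, nurse, physiotherapy, outpatient, inpatient, emergency) unrestricted, since attaching the new phrase to them would narrow what Section 11.1 now collects. In Section 11.4, say that this same set of medication is what will be valued.

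The cost is one reworded phrase, one reworded sentence and a slightly longer questionnaire item. No visit, instrument or clinical rule changes.

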11.3 Quality of Life

Participant health-related quality of life data will be collected using the EQ-5D 5L as described in Section 6.2 on Outcomes.

11.4 Cost effectiveness

The economic evaluation will be conducted from an NHS perspective. All resource use will be valued in monetary terms using appropriate unit costs. Unit costs for primary and secondary care resources will be taken from the PSSRU Unit Costs of Health and Social Care publication [39]. Any medications used by participants will be valued using the British National Formulary [40]. Total and mean cost per participant will be calculated for each group using methods to account for uncertainty around the mean estimates of costs [41].

Quality Adjusted Life Years (QALYs) will be calculated from EQ-5D-5L data using the recommended tariff values [28].

The primary economic evaluation will be a within trial cost utility analysis. Analysis will be completed as intention to treat, based on randomised group. Costs and QALYs will be combined to calculate the incremental cost per QALY gained along with the incremental net benefit [42].

In addition, a Markov decision model with a monthly cycle will be employed to evaluate effects of the intervention on costs, QALYs and cost-effectiveness over a 5-year horizon. Trial data will be supplemented with data from our existing studies of PFMT and pessary for prolapse [5,6,21] to develop the health states and identify suitable transition probabilities. All costs and outcomes beyond 1 year will be discounted at 3.5% [43].

12 EMBEDDED PROCESS EVALUATION

12.1 Overview

A mixed-methods process evaluation will address the three key process evaluation functions: context, implementation and mechanisms of action [44]. Context, a core element of the MRC complex intervention framework [14], will be explored in terms of the personal, organisational, trial and problem contexts [22]. Implementation will be considered 'in the light of NPT' (Normalisation Process Theory) [45] (May et al, 2018 p18), with specific focus on fidelity to the intervention; acceptability of the intervention; adherence to the intervention within care delivery and by the participant. These components can be cross referenced to cognitive participation, coherence and collective action with the NPT. Mechanisms of Action, or the initial Programme Theory as expanded within the new MRC framework, is outlined in Figure 1. Table 3 below links the data collection methods to the process evaluation functions.

IRAS ID: 338183 PEPPY protocol version 3.0 26/02/2025 ISRCTN: xxxxxx Page 30 of 51

Table 3. Process evaluation data collection and links to process evaluation function

| Functions | Types of data collection | | | | |
|-----------------------------|----------------------------------|-----------------------|---|---|---|
| | (25 intervention, 25 control) | trial participants | staff who recruit or deliver the intervention | | Completion of NoMAD tool (n=39 approx.) |
| Context | X | | | X | X |
| Implementation – fidelity | | Х | Х | Х | |
| Implementation – acceptance | X | | | | |
| Implementation – adherence | X | | | X | |
| Programme Theory | | | | | |

Shaded box indicates that the method is a main source of data for the process evaluation function; the unshaded boxes (marked with x) indicate a subsidiary source of data for the process evaluation function.

12.2 Sample, recruitment, consent and data collection

The sample, their recruitment and consent and data collection for each of the five components is described below.

12.2.1 Audio-recordings of PFMT plus pessary and PFMT alone participant appointments to assess intervention implementation and fidelity

We will aim to record 50 participant/clinician intervention appointments (25 in the PFMT plus pessary group and 25 in the PFMT alone group). Approximately 3-5 of these appointments in each group will be recorded within the pilot study. Variance within the sample of recordings will be aimed for, based on: centre (at least one recording per centre); appointment number (ensuring representation across appointments 1-5); women's age (to maximise range); and treating clinician (variation in individual clinicians).

Treating clinicians will be asked to agree to appointment recording as part of the SIV, and will be asked to sign consent (Consent Form 06). Information about recording of some appointments is contained within the main trial PIL for women (PIL 01). Participants will indicate if they consent to appointment recording on their main trial consent form (by initialling box). The Process Evaluation researcher will check if a woman has consented to recording before asking the treating clinician to record the appointment. The treating clinician will verbally reconfirm consent with the woman prior to the recording.

With consent in place, small digital recorders will be placed in the consulting room or phone call recorded to gather all instruction given.

12.2.2 Qualitative semi-structured interviews with trial participants to explore context, fidelity, acceptance, adherence and programme theory

In order to achieve information power [46], 30 trial participants will be interviewed (15 PFMT plus pessary group, 15 PFMT alone group). Approximately 3-5 of these interviews in each group will be undertaken as part of the pilot study. Sampling will be maximum variation with variance on: woman's age (as wide a range as possible); ethnicity (ensuring representation from varied ethnic groups); prolapse severity (all levels of severity recruited); centre (district general hospital, university hospital, community clinic).

The main trial PIL (PIL 01) introduces the interview study, women are then asked to consent to receiving further information about the interview study. The PE team will review participants who indicate 'yes' on the trial consent form and invite a sample of participants, aiming to

IRAS ID: 338183 PEPPY protocol version 3.0 26/02/2025 ISRCTN: xxxxxx Page 31 of 51

achieve the maximum variation outlined above. Those invited will receive a letter of invitation (Letter 03), a PIL (PIL 03) and a consent form/e-consent form (Consent Form 03). The PE researcher will contact the woman a few days later to ask if she is willing to be interviewed. If yes, she will be asked to verify her preferred method of providing consent (paper or electronic), and then sign and return the consent form in the stamped addressed envelope provided or complete an e-consent. If the participant prefers e-consent, they will be sent an email with a link to a GCU secured REDCAP consent form. On receipt of the form, a PEPPY researcher will check it and if it is complete they will counter sign the consent form and return a copy to the participant. Only when consent has been received and counter signed will the first interview be arranged.

Interviews will take place with the same woman at baseline and at 12 months. Interviews will be undertaken in the medium preferred by the participant: face-to-face, MS Teams/Zoom or phone and each interview will last approximately 1 hour. With consent, all interviews will be audio-recorded. Interview schedules have been developed with PPI input, ensuring EDI principles and mindful of the components of NPT. Topics for discussion include: views on recruitment; the problem (prolapse) and personal context; fidelity to, acceptance of and adherence to the allocated intervention.

12.2.3 Interviews with staff who recruit to the trial or deliver the PFMT plus pessary and the PFMT alone interventions to explore context, fidelity, acceptance, adherence and programme theory

In order to achieve information power, at least two staff members from each centre (at least one of whom is responsible for delivering the intervention, both PFMT and pessary fitting) will be interviewed (approximate target n=26). Approximately 5 recruiters (one from each pilot centre) will be interviewed as part of the internal pilot. Sampling will aim for diversity in centre and staff professional group.

The PE researcher will identify recruiters and treating clinicians from the delegation logs at centres. Potential participants will be sent an invitation email (Letter 04), PIL (PIL 04) and econsent link to the consent form that is hosted on a GCU secured REDCAP platform (Consent Form 04). On receipt of the fully completed e-consent the PE researcher will check the form, countersign it and return a copy of the completed consent to the participant. The PEPPY researcher will then contact the participant to arrange the interview.

Interviews will be undertaken by MS Teams/Zoom or by phone, will be audio-recorded and will last approximately 30 minutes. For recruiters, interviews will focus on factors that influence recruitment, including organisational context. For those who have been involved in delivering PFMT, with or without pessary, and fitting pessaries, interviews will focus on: problems, organisational and trial context; fidelity to, acceptance of and adherence to delivery of the interventions; and views about the programme theory.

All audio files will be deleted from the secure server once data analysis is complete.

12.2.4 Open question in the questionnaire booklet (acceptance, programme theory)

A single open question will be included in the 6 and 12 month follow-up questionnaires sent to all women in the sample to ask about their views on the intervention they have received. These data will be used to refine the programme theory.

12.2.5 Completion of the NoMAD instrument (NPT, programme theory)

Staff at each centre who manage services and deliver the PFMT plus pessary intervention (identified through delegation logs and at SIVs) would be asked to complete the NoMAD (Normalisation Measure Development) questionnaire prior to the intervention being delivered in their area of practice [47]. The introductory information on the questionnaire explains that questionnaire completion is taken as consent. At the end of intervention delivery for all participants within a centre, those who have been involved in delivering and managing IRAS ID: 338183

PEPPY protocol version 3.0 26/02/2025

ISRCTN: xxxxxx Page 32 of 51

intervention delivery (based on the delegation log) will be asked to complete the NoMAD questionnaire. NoMAD is a validated 20-item tool, that maps onto NPT constructs, and aims to assess activity related to how staff, individually and collectively, work to normalise a new intervention within their working practices [47]. The tool has questions that cover the four NPT constructs and their sub-constructs. The instrument will be adapted, as advised, to focus on the PFMT plus pessary intervention.

Descriptive statistics will be used to present findings on individual items of the NoMAD questionnaire. Where individuals have completed the survey prior to intervention delivery and then again at the end of the intervention period, change in paired responses will also be described. We will compare responses across centres and between those who deliver and those who manage delivery of the intervention.

13. ORGANISATION: TRIAL MANAGEMENT AND OVERSIGHT ARRANGEMENTS

13.1 Trial office in Glasgow

The Trial Office is in the Research Centre for Health (ReaCH) based within the School of Health and Life Sciences, Glasgow Caledonian University and provides day-to-day support for the recruiting centres and the running of the trial generally. The Trial Manager will take responsibility for the day-to-day transaction of trial activities, for example approvals, centre set-up and training, oversight of recruitment and follow-up rates etc. The Data Coordinator will provide administrative support to the trial, including organising all aspects of the questionnaires (mailing, tracking, and entering returned data using the trial web data entry portal). The Process Evaluation Researcher in also based in the Trial Office facilitating coordinated working across the trial and the PE.

IRAS ID: 338183 PEPPY protocol version 3.0 26/02/2025 ISRCTN: xxxxxx Page 33 of 51

The Trial Office Team will meet formally at least fortnightly during the course of the trial to ensure smooth running and troubleshooting.

Local organisation at centres

At each centre the local PI and research nurse(s) are responsible for all aspects of local organisation including identifying potential recruits, consenting, completing and maintaining appropriate documentation. The centre agreement documents the full list of responsibilities for centres. Appropriate members of the local team are knowledgeable about the Protocol and will have appropriate Good Clinical Practice (GCP) training if applicable. A trial-specific delegation log is prepared for each centre, detailing the responsibilities of each member of staff working on the trial. The local team is also responsible for notifying SAEs to the Trial Office (see section 8).

Project Management Group (PMG)

The trial is supervised by its Project Management Group (PMG). This consists of the grant holders and Trial Office staff. Observers may be invited to attend at the discretion of the PMG. The PMG will aim to meet/teleconference every month initially, then every 2 months.

The research team has the expertise to provide the pelvic floor dysfunction knowledge and trial/process evaluation/health economics methodology aspects of the research.

The process evaluation sub-group of the research team (including PPI members) will have oversight of the process evaluation analysis.

Trial Steering Committee (TSC)

A Trial Steering Committee (TSC), with independent members, oversees the conduct and progress of the trial. The TSC Charter documents the terms of reference of the TSC, the template for reporting and the names and contact details of members of the TSC. This Charter is filed in the TMF.

Data Monitoring and Ethics Committee (DMEC)

An independent Data Monitoring and Ethics Committee (DMEC) oversees the safety of participants in the trial. The DMEC Charter documents the terms of reference of the DMEC and the names and contact details of members of the DMEC. This Charter is filed in the TMF.

Patient and Public Involvement (PPI) 13.6

Throughout the research we will adhere to the UK standards for Public Involvement [49], use the 2023 Public Involvement in Research Impact Toolkit and provide appropriate PPI training if required.

There are two PPI co-investigators. These co-applicants are long-standing members of the research team. They have guided the proposal via their lived experiences and insights.

Additional input into development of this application has come from The Nursing, Midwifery and Allied Health Professions Research Unit, Research Partnership Group (RPG). This diverse PPI group was established in 2018. The RPG indicated that the proposed research focussed on an important topic, and they provided input into the planning of the research design. A survey of POGP members, as key professional stakeholders, also informed this application.

Both PPI co-investigators, along with another PPI representative will sit on the PMG which steers the research and they will be invited to all the PMG meetings. We will have an additional two PPI representatives who will sit on the independent TSC. Our previous work with PPI on TSCs has shown that two (rather than one) PPI member provides mutual support and mentorship. This will mean that the research has input from five PPI representatives.

To support the PPI representatives, a successful PPI model that was incorporated into the TOPSY trial (NIHR 16/82/01) will be used. "The PPI Social" is a virtual setting where all PPI members (PMG and TSC) come together in a social space to connect, discuss the research in

PEPPY protocol version 3.0 26/02/2025 **ISRCTN: xxxxxx** Page 34 of 51 their own space and raise any issues that they would like to be discussed. The PPI social will be facilitated by the Trial Coordinator.

One PPI co-investigator sits on the qualitative sub-group of the PMG and will be involved in analysis and interpretation of the process evaluation data.

With our PPI team members, we will develop a strategy to inform and engage our stakeholders. Our audiences are: women with prolapse; women's support organisations in our centres (e.g., VOCAL and BAME Research Group in Manchester) and nationally (e.g. RCOG Women's Voices); multidisciplinary healthcare professionals who support women with prolapse (e.g. urogynaecologists, women's health physiotherapists, nurses) and the organisations who support them (e.g. Pelvic Obstetric and Gynaecology Physiotherapy (POGP), RCOG, Royal College of Nursing (RCN)); policy influencing organisations (such as NICE); and policy makers such as the All-Party Parliamentary Groups on Older People and Women's Health, and Department of Health and Social Care. In particular, our PPI representatives will advise on the best ways to share information with women who have prolapse.

